- **DESIGN** ALTER is a phase II randomized, open-label trial using a factorial design of high or standard dose rifampicin with or without linezolid for the first 4 weeks of treatment for tuberculous meningitis (TBM). Initial randomization will be to high (35 mg/kg/day) versus standard (10 mg/kg/day) dose oral rifampicin for 4 weeks. After randomization to high versus standard dose rifampicin, participants will undergo a second randomization to linezolid 1200 mg daily versus no linezolid for 4 weeks.
- DURATION 24 weeks
- SAMPLE SIZE 60 participants
- **POPULATION** Participants with definite, probable, or possible TBM, aged \geq 18 years
- SETTING Masaka Regional Referral Hospital, Masaka, Uganda
- **STRATIFICATION** Participants will be randomized with stratification by HIV status and stage of disease (Grade 1 vs. 2 and 3), as defined by the modified British Medical Research Council criteria.
- **REGIMEN** Participants will first be randomized 1:1 to:

High dose rifampicin 35 mg/kg for 4 weeks vs. standard dose rifampicin 10 mg/kg

Participants will then be randomized 1:1 to:

Linezolid 1200 mg daily for 4 weeks vs. no linezolid (see **Table 1**)

In addition, all participants will receive standard treatment for TBM with isoniazid 5 mg/kg/day, pyrazinamide 25 mg/kg/day, ethambutol 20 mg/kg/day, corticosteroids (IV dexamethasone 0.4 mg/kg/day for 1 week, 0.3 mg/kg/day for 1 week, followed by a prednisone taper over 6 weeks), and vitamin B₆ 50 mg daily. After the first 4 weeks of therapy, participants in the high dose rifampicin arm (Arm A) will receive standard dose oral rifampicin (10 mg/kg/day) for another 11 months as per national guidelines.

		RI	F
colid		High dose (35 mg/kg)	Standard dose (10 mg/kg)
inez	+	Arm A: R ₃₅ HZEL	Arm B: R ₁₀ HZEL
	-	Arm C: R ₃₅ HZE	Arm D: R ₁₀ HZE

 Table 1: Study regimens

R, rifampicin; H, isoniazid; Z, pyrazinamide; E, ethambutol; L, linezolid

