4.0 STUDY DESIGN

This is an open-label, randomized clinical trial with a factorial design. Initial randomization will be to high (35 mg/kg/day) versus standard (10 mg/kg/day) dose oral rifampin for the first 4 weeks of intensive therapy. Participants will then undergo a second randomization to linezolid 1200 mg daily versus no linezolid for the first 4 weeks of therapy. We will use a computer generated permuted block randomization (block size = 2 or 4) stratified by TBM grade (1 vs 2 and 3), given the association between TBM severity and mortality. The trial is open label, although we will endeavor for research staff assessing adverse events, neurocognitive and functional outcomes, and PK data to be blinded.

Initiation of high or standard dose oral rifampicin and linezolid or no linezolid will begin immediately (within 24 hours) after randomization. In addition, all participants will receive a standard backbone of oral TB treatment with INH 5 mg/kg/day, PZA 25 mg/kg/day, EMB 20 mg/kg/day, corticosteroids (IV dexamethasone 0.4 mg/kg/day for week 1, 0.3 mg/kg/day for week 2, followed by a prednisone taper over 6 weeks), and vitamin B₆ 50 mg daily. After the first 4 weeks of therapy, participants will receive standard dose oral RIF (10 mg/kg/day) for another 11 months along with standard treatment for TBM per national guidelines. Patients admitted to Masaka Regional Referral Hospital who meet eligibility criteria will be invited to participate.

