4.1.7 Randomization

At study entry and prior to the 4th dose of TB treatment, participants will first be randomized by a computer-generated permutated block randomization (block size of 2 or 4) with a 1:1 randomization to high (35 mg/kg) versus standard dose (10 mg/kg) rifampicin. A second 1:1 randomization will then be performed to linezolid 1200 mg daily or no linezolid. Randomization will be stratified by British Medical Research Council (BMRC) TBM disease grade (Table 2), determined at the time of consent, given the association between worse disease severity and higher mortality¹.

Table 2. British Medical Research Council (BMRC) TBM disease grade

GRADE I	Glasgow coma score 15, no focal neurological signs
GRADE II	Glasgow coma score 11–14 with or without focal neurological sign or Glasgow coma score 15 with focal neurological signs
GRADE III	Glasgow coma score \leq 10 with or without focal neurological signs

The randomization schedules will be provided to the site pharmacy in a listed sequence. The sequential, unique randomization code will be recorded on the study entry CRF to assure there is no

skipping of the randomization order. All randomized participants will initiate their allocated study TB treatment within 24 hours of randomization and ideally the same day. For participants from whom informed consent has been obtained, but who are deemed ineligible or who do not enroll into the protocol, a Screening Failure form must be completed and entered into the database.

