5.7 Antiretroviral Therapy

In a randomized trial of TBM participants in Vietnam, immediate ART did not improve survival and was associated with significantly more grade 4 adverse events compared with delayed ART initiation at 8 weeks.⁴⁶ As there is no available evidence that earlier ART confers a survival advantage, the international standard for ART initiation in persons living with HIV with TBM is currently at about 8 weeks.⁴⁶ HIV-infected participants not already receiving ART will be recommended to initiate ART at about 8 weeks after TB treatment initiation according to international guidelines. For persons on ART presenting with virologic failure, they would switch regimens at about 8 weeks after initiation of TB treatment. Appropriate counselling will be undertaken in HIV clinics. ART regimens will be prescribed and provided per National HIV Treatment Guidelines. HIV-infected participants will receive cotrimoxazole prophylaxis, unless allergic. We expect that the majority of our HIV-infected participants will not be receiving ART at TBM presentation; according to WHO guidelines they will be offered ART 8 weeks after starting TB treatment. Earlier initiation of ART is associated with an increase in adverse events and does not reduce mortality.³⁶ Early ART is associated with immune reconstitution inflammatory syndrome (IRIS), which can be fatal in TBM. Patients who are culture positive for *M. tuberculosis* from CSF at TBM diagnosis are also at increased risk of TBM-IRIS.³⁷

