8.1.2 Hematological toxicity

A hematological toxicity management plan will be implemented if any of the following criteria are met:

- Hemoglobin < 7.0 g/dL for men, <6.5 g/dL for women
- Platelets <50,000/mm³
- Absolute neutrophil count <600/mm³

Management plan:

1. Discontinue linezolid

- 2. Assess for use of other myelosuppressive medications and discontinue non-essential medications (e.g., co-trimoxazole)
- Repeat blood count will be performed every 2 (+/-1) days until stable. If the abnormal hematological parameter(s) returns to Grade <2 and any associated symptoms resolve, linezolid 1200 mg can be restarted.
- 4. Continue to follow blood count every 2 (+/-1) days until stable. If after restarting linezolid, the abnormal hematological parameter returns to the above criteria, linezolid should again be discontinued.
- 5. Continue to follow blood count every 2 (+/-1) days until stable. If the abnormal hematololgical parameter(s) returns to Grade <2 and any associated symptoms resolve, linezolid can be restarted at 600 mg daily.
- 6. Continue to follow blood count every 2 (+/-1) days until stable. If after restarting linezolid, the abnormal hematological parameter returns to the above criteria, linezolid should be discontinued permanently.

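### The synopsis stratifies randomisation by HIV status and grade, sections 4.0 and 4.1.7 by grade only, and nothing says which scheme the allocation lists follow

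*Combined protocol and SAP*

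**What the plan says.** The protocol describes the stratification in three places.

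- **Synopsis, Stratification:** "Participants will be randomized with stratification by HIV status and stage of disease (Grade 1 vs. 2 and 3"). Two binary factors give 2 × 2 = 4 strata.
- **Section 4.0:** "stratified by TBM grade (1 vs 2 and 3), given the association between TBM severity and mortality". One binary factor gives 2 strata. The lists use permuted blocks of size 2 or 4.
- **Section 4.1.7:** "Randomization will be stratified by British Medical Research Council (BMRC) TBM disease grade (Table 2), determined at the time of consent". HIV is not mentioned. The linezolid allocation follows the rifampicin allocation: "A second 1:1 randomization will then be performed to linezolid 1200 mg daily or no linezolid".

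Two further statements connect HIV to the haematological outcome. Section 5.7: "HIV-infected participants will receive cotrimoxazole prophylaxis, unless allergic". Section 8.1.2, in the plan for low blood counts: "Assess for use of other myelosuppressive medications and discontinue non-essential medications (e.g., co-trimoxazole").

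Section 10.2 makes Grade 3 or higher myelosuppression over the 4 weeks the lead outcome of the adverse event evaluation. It is compared between linezolid and no linezolid by a Cochran-Mantel-Haenszel (CMH) test across rifampicin dose. Section 10.2 says this test accounts for the stratified randomisation, but the only stratum it names is rifampicin dose.

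**The concern.** Section 4.1.7 has the schedules supplied to the site pharmacy as a listed sequence, so the strata must be settled before any list exists. With two schemes in one protocol, there is no fixed standard against which to judge the lists. Section 11.5 makes departures from randomisation procedures reportable, and such a departure cannot be defined here. A report that follows the synopsis could also describe a design that was not used.

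HIV is an awkward factor to leave open. It brings a co-treatment that the protocol itself lists as myelosuppressive, and myelosuppression is the outcome on which the 30 versus 30 comparison is powered. If the lists ignore HIV, an uneven split could add to or mask a linezolid difference in that outcome, and the stated analysis does not clearly adjust for it.

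**Working it through.** **Inputs from the documents.** Total 60, with 30 per linezolid group (section 10.1); two 1:1 allocations, so 60/4 = 15 per factorial cell; blocks of 2 or 4; assumed myelosuppression 40% versus 10%, alpha 0.05.

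**Input assumed.** HIV prevalence p. The documents give no share. The inclusion criteria do not require HIV, while section 7.4 describes a population with advanced HIV. The range shown is 50 to 95%.

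**1. The plan's own figure.** Power for 40% versus 10% with 30 per group, two-sided 0.05 (the section does not state the number of sides), is 78.0% (pooled normal), 79.6% (exact power of the uncorrected chi-square), 80.3% (arcsine) or 81.6% (unpooled normal). The stated 80% is reproduced to within the choice of method. The stratification question does not alter it.

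**2. Chance of HIV imbalance if HIV is not stratified.** The threshold is a difference of 6 or more of 30, that is 20 percentage points. Two models are used, neither of which models the blocks.

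- Independent counts: X₁, X₂ ~ Binomial(30, p), P(|X₁ − X₂| ≥ 6).
- Total fixed at H = 60p: K ~ Hypergeometric(60, H, 30), P(|2K − H| ≥ 6).

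| HIV prevalence | Independent | Total fixed |
|---|---|---|
| 50% | 15.5% | 19.6% |
| 60% | 14.7% | 18.7% |
| 70% | 12.0% | 15.8% |
| 80% | 7.5% | 10.4% |
| 90% | 1.8% | 2.4% |
| 95% | 0.2% | 0% |

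For the exploratory rifampicin contrast within linezolid (15 versus 15), a difference of 4 or more (27 points) has probability 20.0%, 19.1% and 16.1% at 50, 60 and 70% with independent counts. With the total fixed the figures are 14.3%, 26.4% and 10.9%; they jump because the counts are discrete.

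**3. What a 20-point imbalance does to the outcome.** Take 80% HIV-positive in one group and 60% in the other, with no linezolid effect. The risks by HIV status are assumptions.

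- Risks 20% (HIV-positive) and 5% (HIV-negative): 0.8 × 0.20 + 0.2 × 0.05 = 0.17, against 0.6 × 0.20 + 0.4 × 0.05 = 0.14. The crude difference is 3 points. Type I error of the unadjusted chi-square, given this split, is 6.4%, against 5.2% when balanced.
- Risks 30% and 5%: 0.8 × 0.30 + 0.2 × 0.05 = 0.25, against 0.6 × 0.30 + 0.4 × 0.05 = 0.20. The difference is 5 points, and the error is 7.3% against 4.9%.

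The planned difference is 40 − 10 = 30 points.

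**4. What HIV stratification gives.** A permuted-block list with blocks of at most 4 can be out of balance by at most 2. If there is one linezolid list per stratum, HIV-positive participants come from two lists (one per grade group), so their counts differ by at most 2 × 2 = 4 of 30, about 13 points. If the linezolid lists are also separate within each rifampicin arm, the bound is 4 × 2 = 8 of 30. These are worst cases. The structure of the second randomisation should therefore be stated as well.

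**The case against.** The strongest reply is that this is a drafting mismatch with little statistical consequence. Grade alone is a defensible choice, and sections 4.0 and 4.1.7 give a reason for it. The lists may already follow the synopsis, in which case a phrase is simply missing from two sections. Even if they do not, randomisation keeps the test valid over all allocations; what remains is conditional bias in an unlucky split and some lost precision, at 3 to 5 points against a planned 30. If nearly all participants have HIV, large imbalance becomes rare. All of this stands, and it limits the size of the harm. It does not settle which scheme is in force.

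A reader might infer more than the documents support:

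- **That the lists were built from sections 4.0 and 4.1.7.** The protocol does not say so.
- **That HIV is an established predictor of myelosuppression in this trial.** This is an inference from sections 5.7 and 8.1.2; no rate by HIV status is given.
- **That the primary results are at risk.** The primary endpoints are linezolid PK parameters, and nothing in the documents shows that HIV alters them. Myelosuppression falls under a secondary objective. The rifampicin contrast within linezolid is only to be explored, and section 10.1 concedes that it may lack power.

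**Conclusion.** The contradiction is plain and unresolved: four strata in the synopsis, two in the body. It needs correcting because an allocation scheme must be specified once and reported as used.

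The statistical consequence is conditional on grade-only lists, and it is modest. At 50 to 70% HIV prevalence, the chance of a 20-point HIV imbalance between the linezolid groups is 12 to 16%, or 16 to 20% with the total fixed; it is about 7 to 10% at 80% and about 2% at 90%. Such an imbalance could modestly distort the secondary myelosuppression comparison. It would not invalidate the test, and the PK endpoints are not shown to be affected. The prevalence range and the risks by HIV status are assumptions; the conflict between the sections is not.

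**What to change.** State one stratification scheme in the synopsis, section 4.0 and section 4.1.7, and say whether the linezolid lists are separate within each rifampicin arm.

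- **If lists are not yet issued:** stratify by HIV status and grade, as the synopsis has it. Table 5 places HIV documentation at screening, so the factor is available in time. The cost is regenerating the lists and a few more incomplete blocks. Sample size and stated power do not change.
- **If grade-only lists are in use:** correct the synopsis and prespecify a supportive HIV-adjusted analysis of myelosuppression. This could be a CMH test stratified by HIV status and rifampicin dose (2 × 2 = 4 strata), or logistic regression on linezolid with HIV status as a covariate. Crossing HIV, grade and rifampicin dose gives 2 × 2 × 2 = 8 strata, an average of 60/8 = 7.5 participants each, which is too sparse. CMH takes strata rather than covariates, so this is a real choice of method and should be written down before the outcome data are examined.

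In either case, section 10.2 should name the factors that its CMH test uses when it says that the test accounts for stratified randomisation. Section 10.2 describes no Modified Rankin comparison, so there is no existing analysis of that outcome to which HIV status could be added.

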1.0 BACKGROUND AND STUDY RATIONALE

Although TBM is the most devastating form of TB, it has largely been neglected in the global health research agenda. Even with appropriate therapy up to 50% of patients with TBM die, most within the first month after presentation.¹⁻³ Of those who survive, neurologic disability is common.⁴⁻⁶ Despite these bleak outcomes, a paucity of data exists on the optimal approach to TBM treatment, including for people living with HIV (PLWH).

A targeted approach to TBM management must leverage drugs that penetrate the CNS. In the absence of large-scale trials, the same standard drug regimens and dosing used for pulmonary TB—rifampicin (RIF), isoniazid (INH), pyrazinamide (PZA), and ethambutol (EMB) for two months (intensive therapy), followed by RIF and INH in the continuation phase—are empirically employed for TBM, except with a longer continuation phase to complete 9 to 12 months of therapy. This generic approach assumes that the efficacy of TB drugs is equivalent at all sites of infection, disregarding the unique challenges of infection of the CNS.⁷ Effective drugs for TBM must penetrate the blood brain barrier (BBB) and remain in the CNS to achieve bactericidal drug concentrations.⁸

Rifampicin plays an essential role in the treatment of TBM. Of standard TB drugs, INH and PZA have good CNS penetration, while diffusion is poor for RIF, EMB, and streptomycin, particularly in the absence of meningeal inflammation.^{8,9} RIF is essential for the treatment of TBM, as evidenced by the fact that those infected with rifampicin-resistant Mycobacterium tuberculosis strains have a nearuniversal fatal outcome, even with treatment with second-line drugs in resource-rich settings.¹⁰. However, RIF has poor cerebrospinal fluid (CSF) penetration, with reported CSF concentrations often reaching less than 10% of those in plasma. Furthermore, standard oral RIF dosing for TBM rarely exceeds the minimum inhibitory concentration (MIC) against *M. tuberculosis* in the CSF.⁸ Increasing the systemic dose of RIF is one strategy to improve CNS drug concentrations. A Phase II open label randomized trial in Indonesia demonstrated 50% reduction in TBM mortality with high dose IV RIF (600 mg/day).² Higher RIF exposure in the CSF was strongly associated with survival.¹¹ In contrast, a TBM trial in Vietnam found no significant difference in mortality with high dose oral RIF (15 mg/kg), although the lack of efficacy may have been due to inadequate dosing, as oral bioavailability is about 50% of IV RIF.^{12,13} In a dose-finding study in Indonesia, an oral RIF dose of 1350 mg (about 30 mg/kg) was safe and resulted in a large increase in plasma and CSF exposures (Dian et al), with a trend toward lower mortality among those with definite TBM.¹⁴ High dose RIF is a promising strategy to improve outcomes in TBM.

Higher doses of RIF are well tolerated with a favorable safety profile. We will randomize participants to high (35 mg/kg) versus standard dose (10 mg/kg) oral RIF. The most common side effect of RIF is harmless red discoloration of bodily fluid (urine, tears and CSF). Other well-recognized side effects of RIF include gastrointestinal upset, rash, flu-like syndrome and thrombocytopenia. Drug-induced liver injury occurs in 20% HIV-infected patients on TB treatment. The drugs most commonly implicated are INH, PZA, and RIF. However, transaminitis is only seen in 0-2.5% of patients treated with RIF monotherapy, so INH and PZA are the most likely culprits. RIF oral doses as high as 40 mg/kg once daily for 14 days and doses of 35 mg/kg for up to 12 weeks have been safe and well-tolerated in clinical trials^{15,16}. In the ReDEFINE dose-finding study, oral RIF as high as 30 mg/kg daily (1350 mg) for 30 days were well tolerated without any increase in the incidence of adverse effects¹⁴.

Several linezolid characteristics favor its use as adjunctive therapy for TBM. Although RIF is the cornerstone of treatment of TBM, even with higher dosing to overcome poor CSF penetration, adjunctive therapies that enhance the potential benefit of high dose RIF may be needed to improve outcomes of TBM. Of new or repurposed drugs in the development pipeline for TB, many coming into clinical use (e.g., bedaquiline, delamanid) are highly protein bound and thus may not freely penetrate the BBB.^{7,17} Linezolid (LZD), a member of the oxazolidinone family with *in vitro* activity against TB,¹⁸⁻²² combines superb CNS penetration and excellent oral bioavailability.^{9,23-25} LZD has been included as salvage therapy for drug resistant (DR) TB.²⁶ In extensively DR (XDR) pulmonary TB, 89% receiving LZD achieved culture sterility by 6 months.²⁷ Acquired resistance was uncommon and occurred late, suggesting a high barrier to LZD resistance. Of 30 patients receiving 6 months of LZD 1200 mg, bedaquiline, and pretomanid for DR TB in the Nix-TB trial, 75% achieved culture sterility by 8 weeks.²⁸ Although LZD has largely been used for DR TB, it may also be valuable for drug susceptible TB. Few data are available on LZD use in TBM,²⁹ and none from randomized trials. In retrospective studies, LZD 600 mg BID in adults and 10 mg/kg every 8 hours for children was associated with better neurologic outcomes and lower mortality.^{30,31}

Cumulative toxicity is less of a concern when adjunctive LZD is administered for a short duration.³²⁻³⁴ LZD's narrow therapeutic window has tempered the enthusiasm for its therapeutic utility for TB. While most treatment-limiting toxicities, including myelosuppression, gastrointestinal (GI) symptoms and optic neuropathy, are reversible, some, including a painful, sensory-predominant neuropathy, may be permanent.^{35,36} LZD toxicity is driven by both dose and duration.³⁷ In 796 patients with gram-positive bacterial infections on LZD 600 mg BID, hematologic toxicities correlated with treatment duration, occurring in 5% of patients on LZD for 2 to 4 weeks. Peripheral neuropathy occurred in only 3 individuals with a mean treatment duration of 95 days.³⁸ Among 85 patients with DR TB on LZD, the majority of AEs occurred after 2 months.³³ Of 33 patients on LZD 1200 mg for XDR TB, anemia and GI symptoms were common (~50%) but necessitated discontinuation in only 2 patients within the first month.³⁹ No cases of peripheral or optic neuropathy occurred before 2 months. We will use a short course of adjunctive LZD, which has not been studied in a randomized trial for TBM, early in intensive therapy to augment bactericidal activity during the logarithmic growth phase of TB while minimizing cumulative toxicity.

Linezolid and the CSF compartment

CSF to plasma concentration ratios of 0.6 to >0.9 support good to excellent CNS penetration of LZD. However, the distribution of LZD in the CSF, from small studies of mostly neurosurgical patients, varies substantially. After a one-time dose of LZD 600 mg IV, mean CSF maximum concentrations (C_{max}) ranged from 5.1 to 6.6 ug/mL. At steady state, CSF C_{max} was 1.3 to 7.1 and up to 10.8 µg/mL, and minimum concentrations (C_{min}) were <0.2 to 3.1 and up to 6.1 µg/mL. The ability to achieve adequate CSF concentrations for sufficient duration has been inconsistent. One study found CSF LZD concentrations were >4 µg/mL for the entire dosing interval, while in another few patients reached concentrations >1 µg/mL. The minimum inhibitory concentration for 90% of isolates (MIC₉₀) is generally <0.5 µg/mL.

Although studies have suggested that lower LZD doses may be effective for TB,^{34,40,41} a dose-ranging trial demonstrated doses >600 mg daily are required for optimal effect.⁴² A higher systemic dose will increase the likelihood of achieving adequate concentrations in the CSF, particularly with LZD and RIF drug-drug interactions. We will use LZD 1200 mg daily to maximize peak concentrations while reducing troughs, which correlate with mitochondrial toxicity and AEs.^{42,43} No dose adjustment is needed for renal or hepatic impairment or older age.⁴⁴ We will give LZD for the 1st 4 weeks of intensive therapy to enhance bactericidal activity in the early rapid growth phase when mortality is highest, while minimizing duration-dependent toxicity.

A critical consideration in determining optimal LZD dosing for TBM is LZD RIF drug-drug interactions. As RIF is a potent inducer of hepatic cytochrome P450 (CYP450) enzymes and efflux mechanisms (e.g., P-glycoprotein transport system), RIF can lower drug concentrations with potential loss of efficacy. In addition, with repeated administration, RIF induces enzymes resulting in a decrease in its own concentrations. Although LZD metabolism is independent of CYP450, increased LZD clearance has been observed when given with RIF, with reduced LZD concentrations of up to 30% in healthy volunteers and greater in ill patients. These studies have focused on plasma PK, while the impact of RIF on LZD CSF pharmacokinetics is unknown. We have a unique opportunity to evaluate LZD pharmacokinetics when administered with RIF in TBM patients, in whom various factors (e.g. meningeal inflammation, corticosteroids, critical illness) may influence LZD concentrations. This will be critical to establishing optimal LZD dosing for a Phase III efficacy trial.

STUDY RATIONALE

The current mortality associated with TBM is unacceptably high, particularly among PLWH in low and middle-income countries. The highest proportion of deaths occurs within the first month after TBM treatment initiation, indicating that this time period is critically important when considering improved treatment strategies. RIF, the most important drug in the treatment of TBM, seldom reaches minimal inhibitory concentration for *M.tb* in CSF, which is likely to jeopardize therapy. Furthermore, mortality rates in the aforementioned favorable Indonesian trial still exceeded 33% in the high dose RIF arm, arguing that adjunctive therapies may be needed to further enhance the potential benefit of high dose RIF. Adjunctive linezoild in the first month of TBM treatment, when the highest proportion of deaths occurs, may allow us to augment bactericidal activity during the critical rapid growth phase of TB while minimizing cumulative toxicity. Because of drug-drug interactions (DDI), evaluating LZD pharmacokinetics (PK) when administered with RIF will be critical to establishing optimal LZD dosing for an efficacy trial. In this trial, we will examine CSF and plasma LZD PK in the presence of high or standard dose RIF and will evaluate LZD safety and tolerability in TBM patients living with HIV from an African population, correlating adverse events (AEs) with LZD exposures.

